Randomized control trial: We will recruit 25 patients with chronic SCI and chronic focal neuropathic pain (>6months) below level of injury who have failed multiple pharmacological agents. Pre-study data collection will include subjective description of pain, baseline visual analog scale (VAS) and numeric pain rating scale (NPRS) values, LANNS pain score survey to accurately determine source of pain is neuropathic in origin, a numerical scale such as World Health Organization Quality of Life- (WHOQOL) brief survey (WHOQOL-BREF) that measures quality of life parameters, subjective SCIM (spinal cord independence measure) scores, SCI specific pain measures (MPI-SCI), and pain diagrams will be obtained on each participant. Written informed consent will be obtained. Each participant will be randomized to one of two sequences:

Sequence 1: C8P application followed by one reapplication of a low dose capsaicin control patch (0.025% Well Patch) (available over the counter)

OR

Sequence 2: Control patch (0.025% Well Patch) followed by one replication of C8P. as indicated in Table 1. Measurements of the primary outcome of pain (VAS) will occur every 2 weeks and all secondary outcomes will be measured at 4,8 and 12 weeks within each period in each sequence.

Substudy: Non-randomized, non-controlled sub-study: We will also have a non-randomized non-controlled sub-study to increase data obtained to help calculate Number needed to treat and minimal clinically important difference for the RCT. Patients with SCI undergoing patch as routine medical treatment for refractory neuropathic pain will be recruited and enrolled immediately after patch application. Subsequently, they will be be followed for a 12 week period using the identical protocol of sequence 1 in the RCT, without reapplication of a control patch.

Clinical Relevance: Potentially giving analgesic pain relief for spinal cord focal peripheral neuropathic pain without the hand strength or dexterity required to open bottles, take oral tablets/capsules, or apply a transdermal patch, cream or ointment on a daily basis.

Item 3 Background

Describe past experimental and/or clinical findings leading to the formulation of your study. For research involving unapproved drugs, describe animal and human studies. For research that involves approved drugs or devices, describe the FDA approved uses of this drug/device in

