RCT: Pre-study data including subjective description of pain, baseline VAS, LANNS and NPRS. Pre-study data collection will include an intake form with subjective description of pain, baseline VAS / LANNS/NPRS, a numerical scale such as SF36 that measures quality of life parameters, subjective FIM scores, and pain diagrams will be obtained on each participant via the outpatient spinal cord injury clinic, or inpatient spinal cord injury unit.

Substudy: Non randomized, non-controlled arm: no pre-study data collection.

RANDOMIZATION: (RCT only)

Randomized dual balanced 2-sequence 2-treatment, 3-period, crossover study (see Table 1).

Tale 1. The proposed study layout

	Period	
Sequence	1	2
1	Α	В
2	В	Α

Where A indicates 8% Capsaicin and B indicates Low dose capsaicin control patch [1]. Each treatment period will be 12 weeks in duration. The proposed design is a standard 2-period, 2-treatment, 2-sequence design. Inclusion criteria: >1year post SCI, chronic neuropathic pain with VAS>3, pain below the level of injury and failure of at least 3 oral or topical pharmacological agents. Exclusion criteria: painful area >1120cm² (4 patches), skin breakdown over area and uncontrolled hypertension.

Methods:

RCT: Each participant will be randomized to one of two sequences:

Sequence 1: C8P application followed by one reapplication of a low dose capsaicin control patch (0.025% Well Patch) (available over the counter)

ÒR

Sequence 2: Control patch (0.025% Well Patch) followed by one replication of C8P, as indicated in Table 1.

Patch application method: Per manufacturers' application directions, the painful area will be treated with topical lidocaine

2.5%/prilocaine 2.5% for 1 hour prior to application of the test patch(es). Active and control patches will then be applied and left in place for one hour. After removal, the cooling gel will be applied to decrease any burning sensation from the capsaicin, per manufacturers' protocol. Blood pressure will be monitored every 30minutes after the capsaicin (control or treatment) patch over the hour of application.

Substudy: Non-randomized, non-controlled prospective arm: Patients with SCI undergoing patch as routine medical treatment for refractory neuropathic pain will be recruited and enrolled immediately after patch application. Subsequently, they will be followed for a 12 week period using the identical protocol of data collection post patch application in the RCT, without reapplication of a control patch.

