Post patch application data collection (RCT and substudy): Measurements of the primary outcome (VAS) will occur every 2 weeks and all secondary outcomes will be measured at 4, 8 and 12 weeks within each period in each sequence. Every 2 week VAS scores will be collected via phone at weeks 2,6,10 and in person at weeks 4, 8, 12. All secondary outcomes surveys will be done at a face to face visit at weeks 4, 8, 12.

Outcome measures: (RCT and substudy)

: Primary efficacy endpoint is the visual analog scale (VAS) score at the end of each of the three 12-week periods (at weeks 12 and 24). Secondary outcome measures include the Multidimensional Pain Inventory (MPI) Pain Severity Subscale, MPI-SCI, International SCI Pain Basic Data Subset (SCIPBDS), WHOQOL-BREF, Spinal Cord Independence Measure (SCIM) and number of concomitant pain medications

Specific Aims

- 1. Determine the effect of the capsaicin 8% patch on VAS scores.
- 2. Determine the effect of the 8% Capsaicin (C8P) on QOL.
- 3. Determine the effect of the C8P on physical function. .

UHS clinic sites: Patients will be approached by providers (who are also investigators in this study), regarding being contacted by phone to hear more about the study. If agreeable patient's name and phone number will be provided manually/verbally to the study team at the VA in order to contact interested patients. No PHI will be transferred electronically between UHS and the VA. Data for the study will be provided by patient and collected at the VA.

Data Analysis Plan:

RCT: Due to the small population of individuals with a spinal cord injury and high incidence of neuropathic pain in such persons and lack of prospective studies on the capsaicin 8% patch, we felt a small group of 25 patients was large enough to show possible potential benefits, small enough to realistically complete this study, follow patients appropriately according to standard of care, and in congruence with the small population size commonly seen in spinal cord injury studies. This study will serve as pilot data for a larger study in the future.

Substudy: Non-randomized, non-controlled arm: 50 participants will be enrolled and we will use the baseline and post patch application data to help determine the number needed to treat and minimal clinically important difference for the RCT.

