RCT and substudy: Data analysis will be performed on subjective description of pain at baseline from NPRS, VAS and evaluated at 2, 4, 8, 12 weeks post application to determine efficacy of capsaicin 8% patch in regards to point value and percentage of reduction compared to baseline. Longevity as recorded by reduction in baseline NPRS and VAS scores in days, weeks, and months of relief until pain returns to baseline. We will also compare our quality of life scale (WHO-QOL) and SCIM scores from pre study to post study and evaluate for more subjective measures of improvement in quality of life and functional improvement respectively. In the RCT trial we will assess for significant differences is outcomes between the treatment and control groups over time whereas, in the non-randomized, non-controlled trial we will compare baseline scores to 12 weeks post patch application scores for all outcomes. The significance of variation in the mean outcome with treatment will be assessed with a mixed effects linear model of the outcome in terms of sequence, subject nested in sequence, period, treatment, and first order carryover. All statistical testing will be two-sided with a significance level of 5%. SAS Version 9.4 for Windows or later, SAS Instititue, Cary, North Carolina, or R will be used throughout.

0

15-322H, [name], Form BC, 07-24-19, AMD.docx vSept3-2014

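### Item 6 does not supply baselines that its own analysis uses: the RCT list names FIM and (as an example) SF36 instead of SCIM and WHOQOL-BREF, and the substudy has none

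*Combined protocol and SAP*

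**What the plan says.** **RCT, before treatment.** The pre-study section of Item 6 lists VAS, LANNS and NPRS, and then "a numerical scale such as SF36 that measures quality of life parameters, subjective FIM scores, and pain diagrams will be obtained". The Methods in Item 2 give a different list for the same time point: a quality-of-life scale, again worded as an example, namely the WHOQOL "brief survey (WHOQOL-BREF) that measures quality of life parameters, subjective SCIM".

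**RCT, after treatment.** The secondary outcomes in Item 6 include "WHOQOL-BREF, Spinal Cord Independence Measure (SCIM) and number of concomitant pain medications". SF36 and FIM are not among them. On timing, "all secondary outcomes will be measured at 4, 8 and 12 weeks within each period in each sequence".

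**Substudy.** The pre-study section of Item 6 states that nothing is collected beforehand in this arm, and the Methods enrol each patient once the patch is already on.

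**Analysis.** Under a heading that covers both studies, the Data Analysis Plan will "compare our quality of life scale (WHO-QOL) and SCIM scores from pre study to post study". It then separates them. "In the RCT trial we will assess for significant differences is outcomes between the treatment and control groups over time"; the substudy instead compares baseline with week 12 on every outcome. The named model is "a mixed effects linear model of the outcome in terms of sequence, subject nested in sequence, period, treatment, and first order carryover". Earlier in the same plan, substudy baseline and follow-up data are to help determine the number needed to treat (NNT) and the minimal clinically important difference (MCID).

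**The concern.** A change score needs the same instrument at both ends. If site staff work from Item 6, function may be measured with FIM before treatment and SCIM afterwards, and quality of life with SF36 before and WHOQOL-BREF afterwards. Neither pair gives a change.

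The substudy problem is wider. Its comparisons have no control group, so they rest entirely on baseline, and the protocol says that none is collected. This affects VAS as well as the secondary scales, and it carries through to the NNT and MCID work that is the stated reason for the substudy.

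There is also a smaller point of clarity. Aims 2 and 3 concern the effect of the 8% patch on quality of life and physical function. The only analysis sentence that names WHOQOL and SCIM describes a before-after change, and in the RCT that change has no control.

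**Working it through.** The plan gives no figure to reproduce, so the check sets the sections side by side.

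**1. RCT instruments**

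| Place | Quality of life | Function |
|---|---|---|
| Item 2, Methods (pre-study) | WHOQOL-BREF, as an example | SCIM |
| Item 6, pre-study data collection | SF36, as an example | FIM |
| Item 6, outcome measures | WHOQOL-BREF | SCIM |
| Item 6, Data Analysis Plan | WHOQOL | SCIM |

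Three of the four places agree, and the Item 6 pre-study list is the odd one out. After treatment each scale is scored at 3 visits × 2 periods = 6 times per patient, or 6 × 25 = 150 planned SCIM scores if all 25 complete. Under the Item 6 list, none of these has a SCIM starting value. For WHOQOL-BREF the gap is possible rather than certain, because SF36 is offered only as an example.

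**2. Substudy baselines**

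- Planned enrolment: 50.
- Baseline scores collected by the study, per Item 6: 0 for every outcome.
- Analyses that need a baseline: the pre-to-post comparison of WHOQOL and SCIM, the baseline-to-week-12 comparison on all outcomes, and the use of baseline data towards the NNT and MCID.
- Stated source of those baselines: none.

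**3. What the RCT before-after change measures**

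Let p1 and p2 be period effects, tA and tB the effects of the 8% and control patches, and cA and cB their carryovers. Relative to pre-study, the expected week-24 change is:

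- 8% patch first: p2 + tB + cA
- control first: p2 + tA + cB

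By week 24 a patient who completes both periods has had both patches. Within either sequence the change mixes time, the latest patch and carryover from the earlier one, with nothing to subtract. The comparison between treatments does have a control, and it needs no pre-study score.

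**4. Whether the named model delivers that comparison**

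Order the four cells as sequence 1 period 1, sequence 1 period 2, sequence 2 period 1, sequence 2 period 2, and code:

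- sequence S = (1, 1, −1, −1)
- treatment T = (1, −1, −1, 1)
- first-order carryover C = (0, 1, 0, −1)

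Then (S − T)/2 = (0, 1, 0, −1) = C. Intercept, sequence, period, treatment and carryover make five fixed parameters for four cell means. With all of them fixed, the treatment effect is not uniquely estimable. This is a separate defect, but a fix that points to the between-treatment comparison has to mention it.

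**The case against.** **The RCT lists are loosely worded, and Item 2 has the right scales.** This is fair. The Item 6 list says what data collection will include, not what it is limited to, and Item 2 names both scales before the study. The text therefore shows two lists in conflict. It does not show that baseline WHOQOL-BREF and SCIM scores will be missing. What stands is that the list in the detailed procedure is the one that disagrees with the analysis.

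**A reader might infer that the RCT will answer Aims 2 and 3 by a before-after change.** The documents do not support this. The sentence after the before-after comparison applies the treatment-versus-control comparison to RCT outcomes in general, and WHOQOL-BREF and SCIM are listed outcomes. The mixed model is the only named method, and no test is attached specifically to the before-after sentence. One can show that a change pooled over two equal sequences puts zero weight on the difference between patches, but the plan never says that it pools. Only a labelling gap remains.

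**One might also want to tie the comparison to week 12 of each period.** That goes beyond clarification. The plan says the RCT comparison runs over time, these scales are scored at three visits per period, and end-of-period timing is fixed for VAS only.

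**Substudy baselines might come from clinic records.** They might, since the patch is given there as routine care. The documents neither say so nor say whether such records hold these instruments.

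**Conclusion.** Two contradictions hold on the current text.

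- **RCT:** if the Item 6 list is followed, the planned pre-to-post comparison has no matched SCIM baseline and possibly no matched WHOQOL-BREF baseline in 25 patients. VAS and NPRS are unaffected, because both are on the Item 6 list. The randomised comparison is also unaffected, because it does not use a pre-study score.
- **Substudy:** as written, the baseline analyses in 50 patients have no stated source of baseline for any outcome, VAS included, and neither does the use of baseline data for the NNT and MCID. This is the heavier of the two, because that arm has no other comparison.

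The third element is a note on clarity: the RCT before-after change should be called descriptive. It is not a finding that the randomised analysis of quality of life or function is absent.

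The conclusions rest on the wording alone and need no assumed effect sizes or variances. The size of the RCT gap depends on which of the two pre-study lists is used in practice.

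**What to change.** **RCT.** In the pre-study section of Item 6, replace SF36 with WHOQOL-BREF and FIM with SCIM, naming WHOQOL-BREF outright and not as an example. In the Data Analysis Plan, add one sentence: the pre-study to post-study change in the RCT is descriptive, and the between-treatment comparison is the test of the 8% patch on these scales. Do not restrict that comparison to week 12 as part of this change. Note alongside it that sequence, treatment and first-order carryover cannot all be fixed effects in a two-by-two crossover, so the model needs its own correction. The cost is wording only. No visits are added, because Item 2 already lists both scales before the study and Item 6 already scores them in each period.

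**Substudy.** Reconcile the pre-study section with the Data Analysis Plan for all outcomes, including VAS. State that baseline scores come from routine-care records made before application, where they exist. For any outcome without such scores, drop the baseline comparison and its use towards the NNT and MCID, and report post-application scores descriptively. The cost is a chart check in up to 50 patients and possibly fewer patients with a usable baseline.

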Capsaicin 8% patch (Qutenza) is an FDA approved treatment for neuropathic pain in post herpetic neuralgia (PHN). After the FDA approval of Qutenza several studies have been published assessing the efficacy and safety in patients with HIV autonomic neuropathy and PHN. In a meta-analysis examining 2057 persons with PHN and HIV-AN, the proportion of responders with relief (>30% improvement in pain lasting from 2-12 weeks) over a 12-week treatment period was 43% in the C8P group and 34% in the control group, a statistically significant difference.

A retrospective review by [name] and [name] pending publication in the American Journal of Physical Medicine and Rehabilitation also supports that Capsaicin 8% patch provided all three patients in the study had complete relief of pain on average after 2 weeks for an average duration of 169 days.

relation to your protocol.	
Item 4	While low dose capsaicin cream has shown efficacy with minimal side effects in radicular pain of 8 SCI
Purpose and rationale Insert purpose, objectives and research questions/hypotheses here. If you cut and paste from another document, make	persons, short dosing intervals (every 1-4 hours) and poor manual dexterity of persons with SCI (e.g., tetraplegia) can impair efficacy and adherence. Thus the novelty of high dose capsaicin is that a single topical application of the C8P for only 1 hour could potentially provide pain relief for 8-12 weeks.
sure the excerpted material answers the question	

Item 5 Study Population(s) Being Recruited In your recruitment plan, how many different populations of prospective subjects do you plan to target? Provide number: 2 e.g., a population can be individuals with type 2 diabetes controlled with diet and/or a population of healthy controls. Or a population can be individuals attending an education program, etc. List each different population on a separate row and provide a short descriptive label: (e.g., normal-healthy, diabetics, parents, children, etc.) To add rows use copy & paste	Identify the criteria for inclusion :	Identify the criteria for exclusion : 4.

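### The uncontrolled substudy's change from baseline feeds efficacy and NNT with no benchmark or limit on interpretation; make it descriptive and take both from the randomised contrast

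*Combined protocol and SAP*

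**What the plan says.** The last paragraph of the Data Analysis Plan (Item 6) is labelled as covering RCT and substudy together. It states:

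- **Purpose:** pain scores are analysed "to determine efficacy of capsaicin 8% patch in regards to point value and percentage of reduction compared to baseline".
- **RCT comparison:** "In the RCT trial we will assess for significant differences is outcomes between the treatment and control groups over time".
- **Substudy comparison:** "in the non-randomized, non-controlled trial we will compare baseline scores to 12 weeks post patch application scores for all outcomes".
- **Level:** "All statistical testing will be two-sided with a significance level of 5" per cent.

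The only model named has crossover terms (sequence, period, treatment, carryover), which a single arm on one treatment cannot support. No reference value, performance threshold or limit on interpretation is given for the substudy.

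Earlier in the same plan the substudy has a narrower role: "50 participants will be enrolled and we will use the baseline and post patch application data to help determine the number needed to treat", along with the minimal clinically important difference (MCID). Item 2 says the same.

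Item 3 gives the only control response figure in the documents. "In a meta-analysis examining 2057 persons with PHN and HIV-AN", response was defined as ">30% improvement in pain lasting from 2-12 weeks", and the proportion responding "was 43% in the C8P group and 34% in the control group, a statistically significant difference".

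The Pre Study Data Collection section of Item 6 says nothing is collected before the patch in the substudy, and the Methods section enrols these patients just after application.

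**The concern.** The substudy has no control group, so its change from baseline contains whatever C8P does plus everything else that moves pain scores over 12 weeks: expectation, attention, other treatment and regression to the mean. A comparison of week 12 with baseline cannot divide these. The evidence in Item 3 suggests that the non-specific part may be large, since 34/43 = 79% of the responder proportion on C8P was also seen on control.

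The plan attaches the word efficacy to reduction from baseline for both parts and does not say which comparison governs. A significant improvement in the substudy beside a null RCT is therefore foreseeable, and nothing in the text prevents it being reported as evidence that the patch works. The same gap affects the NNT, which is the reciprocal of a difference between treated and control response. The substudy supplies only the treated term.

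**Working it through.** **Figures in the plan.** The substudy size of 50 comes without an effect size, SD, power or null value, so no formula can reproduce it. The one checkable statement is the meta-analysis result. With 2057 patients, z = 0.09/√[p̄(1−p̄)(1/n₁+1/n₂)]. A 1:1 split gives p̄ = 0.385 and z = 4.19; an assumed 65:35 split gives z = 3.98. Both agree with the stated significance.

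**Inputs.** n = 50 and two-sided 5% (Item 6, Data Analysis Plan). Control response of 34%, meaning more than 30% improvement (Item 3). Assumed: this control rate applies to SCI; C8P does no better than control; percentage improvement is roughly normal; the test is paired against zero change. The SD of percentage improvement is not in the documents, so a range is shown.

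**Step 1, mean improvement.** If 34% of patients exceed 30%, then mean = 30 − z(0.66) × SD = 30 − 0.4125 × SD.

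**Step 2, chance of a significant improvement.** Noncentrality = (mean/SD) × √50. The result is P(t > 2.01) on 49 degrees of freedom. The nominal rate in this direction is 2.5%.

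| Assumed SD (points) | Mean improvement (%) | Noncentrality | Significant, n = 50 | Significant, n = 40 |
|---|---|---|---|---|
| 30 | 17.6 | 4.15 | 98% | 95% |
| 40 | 13.5 | 2.39 | 65% | 55% |
| 50 | 9.4 | 1.33 | 26% | 21% |
| 60 | 5.3 | 0.62 | 9% | 8% |

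Intermediate values at n = 50 are 87% at SD 35 and 42% at SD 45. At SD 70 the rate is 3%, close to nominal, because this calibration pushes the mean towards zero as the SD grows. The n = 40 column illustrates dropout; it is not a figure from the plan.

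**Step 3, dependence on normality.** In a simulated mixture, 34% of patients have a mean reduction of 30 to 60% and the rest have none, with a within-group SD of 20 to 40. The test is significant in 38% to 99% of studies. The simulated share exceeding 30% improvement is not exactly 34% (it runs from 21% to 41%). The six settings where it lies between 31.9% and 36.0% give the same range, 38% to 99%.

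**Step 4, NNT.** From the treated rate alone, 1/0.43 = 2.3. Against control, 1/(0.43 − 0.34) = 1/0.09 = 11.1. The treated-only calculation applied to the control patients gives 1/0.34 = 2.9.

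**Step 5, whether a fixed benchmark would rescue the substudy test.** Testing the responder rate exactly against 34% with n = 50 needs at least 25 responders (upper-tail error 0.014). Power at a true 43% is 19.5%. Replacing zero by 34% therefore does not make the substudy a useful efficacy test.

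**The case against.** Several points on the other side are sound.

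- **Stated role.** The substudy's declared purpose is NNT and MCID, the treated-versus-control comparison sits in the RCT, and the study is described as pilot work. A reader might infer that the substudy is a main basis for an efficacy claim; the documents do not say so. But the efficacy wording is in a paragraph that expressly covers both parts, with nothing to limit it.
- **The test is inferred.** The text speaks of significance for the RCT and only of comparing scores for the substudy. A test against zero is the usual meaning of such a comparison at a 5% level, but it is not written down.
- **The 34% is borrowed.** A reader might take it as the response of this trial's own control patients. It comes from PHN and HIV neuropathy, and both parts of this study exclude HIV neuropathy. It is also a responder rate over weeks 2 to 12, whereas the planned comparison is of scores at week 12.
- **Control need not mean inert.** Item 3 does not describe the meta-analysis control. This trial's control patch contains 0.025% capsaicin, and Item 2 reports efficacy of low-dose cream in SCI. The calculation therefore concerns a patch no better than control, not a patch with no effect.
- **Two further inferences fail.** Enrolment at a peak of pain is not shown, as the substudy criteria in Item 5 set no minimum score; regression to the mean is a possibility only. Nor is it shown that the substudy is likelier than the RCT to reach p < 0.05, since 50 against 25 patients does not settle that for a crossover.
- **The NNT wording says help.** The plan does not claim that the substudy alone yields the NNT. It does not name the control rate to be used either.
- **An interval carries the same information as the test.** This is true. The gain from the fix lies in stating which comparison may support an efficacy conclusion.

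**Conclusion.** The point holds as a gap in interpretation. The plan lets change from baseline in an uncontrolled arm count towards efficacy, and that change cannot distinguish C8P from non-specific response.

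The size is conditional. If the cited 34% control rate applies to SCI, C8P only matches control, and no change is the null, the chance of a significant result favouring the patch runs from 98% down to 9% as the assumed SD goes from 30 to 60 points, against 2.5%. A reader might infer that a patch no better than control would often be declared effective. Under the normal model that holds for SDs up to about 45, and the documents give no SD to settle it. The qualitative conclusion needs none of these figures; any appreciable non-specific improvement produces the same ambiguity.

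The NNT consequence is more direct: 2.3 or 11.1 from the same cited rates, depending on whether control response is subtracted. The use for MCID is not challenged here. The randomised comparison in the RCT is unaffected, so this is a cheap improvement.

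**What to change.** In the Data Analysis Plan (Item 6):

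1. State that the substudy change from baseline is descriptive: mean change and responder proportion with 95% confidence intervals, no significance test and no efficacy claim.
2. State that efficacy of C8P, and any NNT, come only from the randomised C8P-versus-control contrast in the RCT.
3. In the substudy paragraph, remove NNT as a quantity obtained from the substudy alone; make the same change in Item 2.
4. Reconcile the Pre Study Data Collection section with the analysis, which needs a substudy baseline. State where that baseline comes from and when it was recorded.

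The first three changes take a few sentences and no new data. The fourth may need a data source to be specified, and the descriptive summaries depend on it.

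The cost is a substudy p-value and a substudy-only NNT. An NNT from a 25-patient crossover will probably be imprecise and should carry its interval. For scale, a parallel two-arm comparison of 34% with 43% needs 458 per arm for 80% power, though that figure does not transfer directly to a crossover.
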